PLWH can be powerful change agents for HIV prevention within communities. Our research suggests that as PLWH receive ART and restore their health, they are motivated to protect their social network members and engage in prevention advocacy (i.e., encourage friends and family to seek HIV testing and care and reduce HIV risk); however, the quality of this advocacy is hampered by challenges related to message content, style and timing of delivery, and the selection of appropriate recipients for advocacy. With effective advocacy training, mobilizing PLWH to be change agents within their networks has the potential to be a “game changer” for HIV prevention, particularly in high-prevalence settings where virtually every family is touched by HIV. In the proposed research, we will conduct a randomized controlled trial (RCT) of *Game Changers*, an 8-session peer-led group intervention that aims to empower and mobilize PLWH to be agents for HIV prevention in their social networks. By decreasing stigma among PLWH and their social network members, as well as training PLWH on key strategies to engage social network members in discussions around HIV, *Game Changers* provides PLWH with the tools to do prevention advocacy and is facilitated by peers who are from participants’ communities and living with HIV. *Game Changers* was developed through an NIMH-funded R34 in partnership with the Infectious Diseases Institute (IDI), a public-private partnership in Kampala that provides care to PLWH, that trains healthcare workers on HIV care and treatment, and conducts research to address the HIV epidemic. As part of the intervention development process, the team conducted focus groups with PLWH and social network members, and engaged with community stakeholders, including a community advisory board. Our pilot RCT with 98 PLWH and 57 social network members revealed promising preliminary intervention effects on reduced internalized stigma and increased HIV-serostatus disclosure to social network members among PLWH, as well as increased condom use and HIV testing among social network members.

The **Specific Aims** are:

1. To conduct a fully powered RCT of *Game Changers* to test intervention effects on the primary outcomes of increased HIV testing, reduced condomless sex, and decreased enacted HIV stigma among social network members of participating PLWH.

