Statistical Power. We calculated power for alter reports of condomless sex at month 18. Based on the pilot, we assume 65% of control alters will report condomless sex at month 18. Starting with 736 alters, and assuming ~15% attrition by month 18 (which is conservative, based on 98% alter retention over 8 months in the pilot, and <10% attrition over 12 months in our other studies in Uganda), we will have 625 alters; accounting for within-ego clustering gives us an effective sample size of 612 for ICC=.01 or 568 for ICC=.05. For ICC=.01, we will have .80 power to detect a group difference of 10.3% (i.e., an intervention rate of 54.7%), and for ICC=.05, we will have power to detect a 10.7% group difference. These differences represent small effect sizes (Cohen's $d = .23\text{--}.24$). For PLWH index participants, using pilot data, we estimate the ICCs of our secondary outcomes to be small-to-moderate (0-.16), and assume 15% attribution and 7 intervention groups (either Game Changers or attention control), with an average cluster size of 12.9 (90 intervention participants/7 groups).^{96, 140, 141} After accounting for within-group correlations, we will have 80% power to detect medium to large differences (.41-.58 SD, based on the outcome) between the study arms at follow-up.

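### At two-sided .05, power for the stated fall in condomless sex from 65% to 54.7% is about .74, not .80, and the printed effect size does not fit that fall

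*Combined protocol and SAP*

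**What the plan says.** Aim 1 in the Specific Aims names three primary outcomes among alters: "increased HIV testing, reduced condomless sex, and decreased enacted HIV stigma among social network members of participating PLWH". The expected direction for condomless sex is therefore downward.

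Under Statistical Analysis, the Statistical Power paragraph sizes the trial on one of the three: "We calculated power for alter reports of condomless sex at month 18". It takes the control rate from the pilot: "we assume 65% of control alters will report condomless sex at month 18". From 736 enrolled alters, about 15% attrition leaves 625. Allowing for clustering within the referring index participant, the effective sample is 612 at an ICC of .01 and 568 at an ICC of .05.

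The resulting claims are:

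- "For ICC=.01, we will have .80 power to detect a group difference of 10.3% (i.e., an intervention rate of 54.7"%
- "for ICC=.05, we will have power to detect a 10.7% group difference"
- "These differences represent small effect sizes", with Cohen's d given as .23 to .24.

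The paragraph gives no significance level, does not say whether the test is one- or two-sided, and does not say how d was obtained from two proportions.

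**The concern.** The variance of a proportion is largest at 50%. A fall from 65% moves toward 50% and a rise moves away from it, so with a fixed sample a fall must be larger than a rise to be detected with the same power. The printed differences look too small for falls. The printed effect sizes also look too large for them.

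A reader would conclude that the trial has a 20% chance of missing a true reduction to 54.7%. If the inputs do not support that, the one design figure offered for the primary outcomes is too favourable. The only other power statement in the plan concerns secondary outcomes in the index participants.

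**Working it through.** **Inputs.** All are from the Statistical Power paragraph, except the 1:1 split of alters (368 per arm), which is in the Specific Aims.

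- Control rate p₁ = .65.
- ICC .01: p₂ = .547, n = 612/2 = 306 per arm.
- ICC .05: a 10.7-point fall gives p₂ = .543, n = 568/2 = 284 per arm.
- Assumed, because it is not stated: two-sided α = .05, z = 1.960.

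**Step 1: the effective sample sizes reproduce.** 736 × .85 = 625.6. With about 3 retained alters per index participant (625/210 = 2.98), the design effect is 1 + (3 − 1) × ICC, that is 1.02 or 1.10. Then 625/1.02 = 612.7 and 625/1.10 = 568.2. The discrepancy does not come from here.

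**Step 2: power for the stated falls.** With p̄ = (p₁ + p₂)/2:

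power = Φ[(|p₁ − p₂| − 1.960 × SE₀)/SE₁], where SE₀ = √(2p̄(1 − p̄)/n) and SE₁ = √((p₁(1 − p₁) + p₂(1 − p₂))/n).

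- ICC .01: p̄ = .5985, SE₀ = .03963, SE₁ = .03941. (.103 − 1.960 × .03963)/.03941 = 0.643, so power = **.740**.
- ICC .05: p̄ = .5965, SE₀ = .04117, SE₁ = .04092. (.107 − 1.960 × .04117)/.04092 = 0.643, so power = **.740**.

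Other formulas do not reach .80:

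| Method | ICC .01 | ICC .05 |
|---|---|---|
| Pooled variance | .740 | .740 |
| Unpooled variance | .743 | .744 |
| Arcsine | .740 | .740 |
| With continuity correction | .712 | .711 |
| Control-arm variance only | .762 | .762 |
| One-sided .05, pooled | .831 | .831 |

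Ignoring clustering altogether (n = 625) gives .749 for the 10.3-point fall.

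**Step 3: differences detectable with .80 power (pooled, two-sided .05).**

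| | Printed | Fall from 65% | Rise from 65% |
|---|---|---|---|
| ICC .01 | 10.3 | 11.1 | 10.3 |
| ICC .05 | 10.7 | 11.5 | 10.7 |

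Both printed differences are the detectable rises. A one-sided .05 test gives detectable falls of 9.8 and 10.2 points, which are not the printed figures either.

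**Step 4: effect sizes.** Cohen's h = |2·arcsin√p₁ − 2·arcsin√p₂|.

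| Change from 65% | h |
|---|---|
| Fall to 54.7% / 54.3% (as printed) | .211 / .219 |
| Fall to 53.9% / 53.5% (detectable) | .227 / .235 |
| Rise to 75.3% / 75.7% | .226 / .235 |

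The h needed for .80 power is (1.960 + 0.842) × √(2/n) = .226 at n = 306 and .235 at n = 284, which is the printed .23–.24. Other conversions of the printed falls do not match at both ends: difference over pooled SD gives .210 and .218, difference over control SD gives .216 and .224, and the log-odds conversion (ln OR × √3/π) gives .237 and .246.

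**Step 5: size of the gap.** A 10.3-point fall at .80 power needs about 352–354 effective alters per arm, against 306. Under lighter attrition, power for the printed falls is about .76–.77 at 10%. At 2%, the pilot's loss over 8 months only, it is about .79–.80.

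**The case against.** The power arithmetic itself is hard to dispute, so the case on the other side concerns what surrounds it.

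*Alpha and sidedness are unstated.* This is true, and .74 depends on the two-sided .05 assumption. But one-sided .05 gives .83 rather than .80, and its detectable falls are not the printed ones. The printed differences are recovered at two-sided .05, only in the other direction.

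*The d may not be Cohen's h.* The log-odds values for the printed falls, .237 and .246, truncate to .23 and .24. The pilot results are mixed on this. For HIV testing, 33.3% against 20.0% is reported as d = .30, which agrees with h (.304) and not with log-odds (.38). For condomless sex the reported d of .76 is not h of the follow-up rates (38.5% against 68.4% gives .61), and the log-odds conversion of those raw rates gives .68. So the convention cannot be settled from the documents. Ordinary rounding of the log-odds values gives .24–.25, so that route still does not reproduce the printed range. The power shortfall does not depend on the definition of d.

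*The primary analysis is a repeated-measures mixed model.* Its power could differ from a month-18 comparison. The power paragraph, however, describes a month-18 comparison and uses no baseline correlation. This limits what .74 says about the final analysis. It does not make .80 correct for the calculation described.

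*Attrition of 15% is described as conservative.* The printed claim is conditional on 625 retained alters, and 10% attrition would still leave power below .80.

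**Conclusion.** The concern holds. From the plan's own inputs, and assuming a two-sided .05 test with equal arms, power for the stated falls is about .74 at both ICCs. The chance of missing a true fall to 54.7% is about 26%, not 20%. The falls detectable with .80 power are about 0.8 points larger than printed. No standard formula tried, one- or two-sided, gives .80 for these falls.

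The agreement of both printed differences and both effect sizes with a rise from 65% suggests that the detectable difference was solved upward and then subtracted from 65%. That explanation is not proven, and the correction does not rest on it.

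The shortfall is modest and only the stated figures change. It should be fixed because no other power figure supports the primary outcomes. The result is a check of the single-timepoint calculation as described, not of the mixed model's power.

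**What to change.** State alpha, sidedness and how the effect size was computed. If the test is two-sided .05, choose one of two corrections:

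- **(a) Keep .80 power.** Restate the detectable falls as about 11.1 points (intervention rate about 53.9%) for ICC .01 and about 11.5 points (about 53.5%) for ICC .05. The printed .23–.24 can then stay, described as Cohen's h. If d was meant as a log-odds conversion, it would become about .26 at both ICCs (.255 and .264) and should be reprinted.
- **(b) Keep the printed falls.** State power of about .74 for 10.3 points (54.7%) and for 10.7 points, and change the effect sizes to about .21–.22, again as Cohen's h.

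Either costs one or two sentences in the power paragraph. Sample size, recruitment and analysis are untouched, and the stated figure becomes slightly less favourable.

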The intervention showed preliminary effects consistent with hypotheses. Among alters at month 5, condomless sex with main partners in the past month decreased by 7.7% (46.2% to 38.5%) in the intervention group vs. an increase of 10.5% (57.9% to 68.4%) in the control group; this was a large effect (Cohen's $d = .76$), despite marginal statistical significance in this underpowered small pilot [OR (95% CI)= 0.3 (.1-1.2), $p=.08$]. Among the 20 alters who were HIV-negative prior to the 5-month follow-up and who were not tested for HIV between baseline and the 5-month follow-up, 5 of 15 intervention alters (33.3%) vs. 1 of 5 control alters (20.0%) reported being tested for HIV post-intervention (in between 5- and 8-month follow-ups), which represents a small-to-medium effect size (Cohen's $d = .30$). In terms of mediators, alters of intervention participants were significantly more likely to report engaging in prevention advocacy discussions (mainly on HIV testing, condom use, and ART) in their social networks ($p=.04$). Note that, because we only interviewed a small number of alters for feasibility rather than to detect effects, we did not interview all alters with whom the PLWH did prevention advocacy, and PLWH did not do prevention advocacy with all alters interviewed. Thus, we would expect effects to be stronger in the proposed study, in which we will recruit a larger number of alters.

Results for PLWH also showed effects consistent with hypotheses. Compared to controls at baseline vs. follow-up, intervention participants were more likely to report engaging in prevention advocacy [b (SE) = 0.4 (0.2), $p = .017$], especially related to HIV testing, condom use, and number of partners (all $p < .05$). Intervention participants were less likely to feel internalized [b (SE) = -0.3 (0.1), $p = .012$] and anticipated HIV stigma [b (SE) = -0.5 (0.2), $p = .011$], and to have concerns about disclosure [b (SE) = -0.3 (0.1), $p = .028$], and were ten times more likely to have disclosed to a main partner [OR (95% CI) = 10.0 (1.5-67.7), $p = .022$], compared to control participants. Moreover, intervention participants were more likely to report that all of their alters had been tested ($p < .10$), and that they disclosed to a greater proportion of alters ($p=.05$). The intervention also had effects on social network structure: intervention participants' networks became denser over time, with more and stronger connections among alters [b (SE) = 0.1 (0.3), $p = .004$].

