Aims 1-3. Primary analyses will use a standard intent-to-treat approach, applying generalized mixed models (linear for continuous outcomes; logistic for binary outcomes) to the repeated-measures data to examine how intervention effects change over time, using an indicator for study arm, timepoint (baseline vs. follow-up), and timepoint by arm interaction to indicate whether change differs between arms. Our statistical methods will be consistent with advances in the analysis of personal network research,^{66, 135-137} accounting for any correlation among participants in the same intervention group sessions, and among alters referred by the same PLWH (ego), by adjusting standard errors for statistical inference tests with a sandwich estimator as implemented in SAS v 9.4.^{96, 138-141} We will use imputation for item nonresponse and account for non-random dropouts using logistic regressions that assign weights to retained participants that are inversely proportionate to the predicted probability of the participant being retained; if dropout is random, analyses will incorporate design effects. In follow-up analyses, we will explore interactions between each potential moderator and arm, including sex (of ego and/or alter, and concordance between the two) to examine if these variables moderate the intervention effects. If interactions with categorical moderators are significant, we will conduct post-hoc simple main effects t-tests with Bonferroni corrections. For continuous moderators,¹⁴² we will graph significant interactions at low and high levels of each score (± 1 SD). We will conduct post-hoc simple main effects t-tests with Bonferroni correction by comparing differences between discrete points on the regression lines. If *Game Changers* shows significant effects on hypothesized mediators (Aim 3), to test mediation we will compare: (a) Aim 1 models, adding baseline measures of mediator(s); and (b) the same models as in (a), adding post-intervention measures of mediator(s).¹⁴³ We will examine whether including post-intervention mediator(s) in (b)

decreases the coefficient for intervention effects on outcomes relative to the corresponding coefficient from (a). We will use a bootstrapping approach to test whether mediators account for effects.^{144, 145}

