Aim 4. We will compare *Game Changers* vs. the attention control group in the marginal cost of decreasing alters' condomless intercourse.¹⁴⁶ Using standard methodologies,¹⁴⁶ we define cost-effectiveness ratio (CER) by the difference in per-capita cost of the intervention versus control group divided by the difference in their average effectiveness: $CER = \frac{\mu_{c2} - \mu_{c1}}{\delta_{e2} - \delta_{e1}}$: μ_{c2} is the per-capita cost of *Game Changers*, μ_{c1} is the per-capita cost of the attention control group, δ_{e2} is the percentage of alters reporting any condomless intercourse, and δ_{e1} is the percentage for intervention alters. We will estimate confidence intervals with bootstrap methods.¹⁴⁷ The analysis will be performed from the provider perspective, as we cannot accurately incorporate patient-incurred costs (e.g., given variation in opportunity cost), but we will track the number and length of time spent by patients in intervention and attention control sessions, and assess transportation time and costs. We will use a micro-costing approach recommended by the US Panel on Cost-Effectiveness in Health and Medicine, tracking all costs associated with implementing *Game Changers* and the attention control as estimated from data collected from IDI Finance (e.g., facilitator compensation) and the team.¹⁴⁸ We will collect data using Drummond's checklist of critical elements and follow best practices to maximize comparability of results with other studies.¹⁴⁹ The cost per resource will be calculated by multiplying the quantity used by unit cost; total cost will be derived by adding individual costs.¹⁵⁰ Fixed (capital) costs (e.g., overhead) will be allocated as the hours per week the premises are occupied for the intervention or attention control group. Capital costs will be annualized using a discount rate of 3% with an assumed lifespan of 30 (buildings) and 10 (furniture) years.¹⁵⁰ The analysis will take into account all intervention or attention control group session costs, but exclude costs incurred by participants (e.g., for time) and associated with research. The facilitators will record time spent on the sessions on simple-to-use forms, identifying each activity (e.g., training, preparation, in-session) and session-related materials (e.g., consumable materials). We will differentiate between intervention development (e.g., training) and ongoing costs. Ongoing costs will be tracked to determine any cost efficiencies over time. Within those, we will differentiate between fixed intervention costs and marginal costs of adding a patient, to provide information for generalizability.

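### Aim 4 defines its effectiveness term as a plain difference in arm percentages, with no baseline adjustment, dropout handling, visit or link to the Aim 1 estimate

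*Combined protocol and SAP*

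**What the plan says.** Statistical Analysis, Aim 4, defines the cost-effectiveness ratio as "the difference in per-capita cost of the intervention versus control group divided by the difference in their average effectiveness". The first effectiveness term "is the percentage of alters reporting any condomless intercourse"; the second "is the percentage for intervention alters". The first percentage has no arm label, and neither has a visit. On uncertainty the paragraph says only: "We will estimate confidence intervals with bootstrap methods".

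The protections for the effect estimate are in a different paragraph, which opens: "Aims 1-3. Primary analyses will use a standard intent-to-treat approach, applying generalized mixed models". That paragraph specifies the model as "using an indicator for study arm, timepoint (baseline vs. follow-up), and timepoint by arm interaction to indicate whether change differs between arms". It adds imputation for item nonresponse and, for non-random dropout, "logistic regressions that assign weights to retained participants that are inversely proportionate to the predicted probability of the participant being retained". Nothing in Aim 4 refers back to it.

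**The concern.** Alters' condomless sex is a primary outcome under Aim 1 and also the denominator of the Aim 4 ratio. Under Aim 1 the arms are compared on change from baseline, with dropout weights. Under Aim 4, read literally, they are compared on observed percentages.

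The ratio is inversely proportional to its denominator, so an error in the effect is passed on and somewhat amplified. The Specific Aims say the ratio is meant to inform policymakers. Two estimators for one outcome can disagree on the same data, and the policy figure would come from the one that ignores baseline and retention data the trial already collects.

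**Working it through.** **Inputs from the documents.** 736 alters, 368 per arm, up to 4 and on average 3.5 per index participant (Specific Aims). Control rate 65% at month 18, about 15% attrition, ICC .01 or .05, detectable difference 10.3 points at ICC .01 (Statistical Power). Pilot alter rates at month 5 (Preliminary Studies).

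**Assumed, not in the documents.** A 65% rate at baseline as well; a baseline/follow-up correlation rho of .4 to .6; the dropout gap D in step 5; a two-sided 5% test in step 1.

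**1. The plan's own figure.** Aim 4 gives none; the nearest is the detectable difference for the same outcome. Retained alters: 736 × .85 = 625.6 (plan: 625). With 3.5 × .85 = 2.975 alters per index participant, the effective sample size is 625/(1 + 1.975 × .01) = 612.9 and 625/(1 + 1.975 × .05) = 568.8, which agrees with the plan's 612 and 568. The 10.3 points does not reproduce. At 306 per arm, 65% against 54.7% gives 74.0% power, and the detectable decrease at 80% power is 11.1 points. That is a separate matter; 10.3 serves below as the plan's yardstick, with 11.1 alongside.

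**2. Chance imbalance at baseline.** SD = sqrt(2 × .65 × .35 × (1 + 2.5 × ICC)/368).
- ICC .01: sqrt(.455 × 1.025/368) = 3.56 points.
- ICC .05: sqrt(.455 × 1.125/368) = 3.73 points.

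**3. Part carried into the follow-up difference** (rho × imbalance).
- Low end: .4 × 3.56 = 1.42 points, or 1.42/10.3 = 14%.
- High end: .6 × 3.73 = 2.24 points, or 2.24/10.3 = 22%.
- Against 11.1 points: 13% to 20%.

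**4. Effect on the ratio, true effect 10.3 points, one-SD imbalance.**
- Low end: × 10.3/(10.3 − 1.42) = 1.16, or × 10.3/(10.3 + 1.42) = 0.88.
- High end: × 10.3/(10.3 − 2.24) = 1.28, or × 10.3/(10.3 + 2.24) = 0.82.

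Baseline as a covariate multiplies the variance of the difference by about 1 − rho²: .84 at rho .4, .64 at rho .6.

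**5. Dropout.** If the gap in condomless sex between dropouts and retained alters differs between arms by D points, the observed difference shifts by .15 × D.
- D = 10: 1.5 points; ratio × 10.3/8.8 = 1.17 or × 10.3/11.8 = 0.87.
- D = 20: 3.0 points; ratio × 10.3/7.3 = 1.41 or × 10.3/13.3 = 0.77.

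**6. Pilot, for illustration.** Condomless sex "decreased by 7.7% (46.2% to 38.5%) in the intervention group vs. an increase of 10.5% (57.9% to 68.4%) in the control group". Difference at follow-up: 68.4 − 38.5 = 29.9 points. Difference in change: 10.5 + 7.7 = 18.2 points. The 11.7-point gap between them is the baseline difference, 57.9 − 46.2. If 40% to 60% of it carries over, the adjusted difference is 29.9 − 4.7 = 25.2 down to 29.9 − 7.0 = 22.9 points. The follow-up difference then overstates the effect 1.19- to 1.31-fold, and the ratio is 16% to 23% too low.

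**The case against.** **Silence is not a decision.** The Aim 4 text never calls its percentages unadjusted, and a model-based percentage would also fit the definition. This stands as to intent. But the adjustment and weighting are written under a heading confined to Aims 1-3, so an analyst following Aim 4 as written would compute observed percentages.

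**Chance imbalance is noise, not bias.** This stands. Its direction is symmetric, it is already part of the follow-up difference's standard error (sqrt((.65 × .35 + .547 × .453)/306) = 3.9 points), and a sound bootstrap interval reflects it. A reader might infer that the plan makes the intervention look more cost-effective than it is; the documents give no ground for a consistent direction.

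**The pilot seems to show a large error.** Taking 18.2 points as the truth gives 29.9/18.2 = 1.64-fold overstatement and a ratio 1 − 18.2/29.9 = 39% too low. That requires the whole baseline gap to carry over, and it rests on a pilot with 57 enrolled alters, measured at month 5 for main partners in the past month. The trial's measure covers the past 6 months. The pilot cannot size the problem here.

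**Aim 1's contrast is not plainly the more reliable one.** With equal variances, a difference in change has variance 2(1 − rho) relative to a follow-up difference: 1.2 at rho .4, 1.0 at .5, 0.8 at .6. Below .5 it is noisier. This stands, and it is why the remedy should be covariate adjustment rather than a difference in change.

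**Borrowing the Aim 1 model would not be enough.** That model gives each arm its own baseline level, so its arm difference in probability at follow-up keeps the imbalance. This also stands and shapes the fix.

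**Dropout may be small.** Statistical Power cites 98% pilot alter retention over 8 months and calls 15% attrition conservative. The documents give no evidence of arm-related dropout, so step 5 is a sensitivity range and not an estimate.

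**Conclusion.** The point holds as a defect of specification with a practical cost. Read literally, Aim 4 yields an effect with no baseline or dropout handling for an outcome that Aim 1 does adjust.

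The imbalance component is a loss of precision: 1.4 to 2.2 points for a one-SD imbalance, 14% to 22% of the planned 10.3 points, given a 65% baseline rate and a correlation of .4 to .6, both assumed. Arm- and outcome-related dropout is the only part that would bias the ratio in a way the bootstrap cannot repair; its size is unknown. The documents do not support a claim that the ratio will be biased in a known direction, or that Aim 1's difference in change is the better estimate at every plausible correlation.

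**What to change.** In Aim 4, define the denominator as a standardised risk difference, control minus intervention, at a named follow-up visit; month 18 is the natural candidate because Statistical Power uses it. Estimate it from a logistic model with baseline condomless sex as a covariate, or from a repeated-measures model with arm means constrained equal at baseline. Use the imputation and inverse-probability-of-retention weights already planned for Aims 1-3. Standardisation is needed because a logistic model yields an odds ratio, while the ratio needs a difference in percentages.

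Refit the whole procedure, weights included, in each bootstrap replicate, resampling whole index participants with their alters and respecting session groups. Label the arm for each percentage. Report the crude difference as a sensitivity analysis. State how the Aim 4 estimate relates to the Aim 1 contrast, since the two need not coincide numerically.

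The cost is a few sentences in the plan and a little extra analysis code. No new data are needed.

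### Aim 4 plans a bootstrap interval on a cost-effectiveness ratio with no rule for effect differences at or below zero; a percentile interval would mislead if the observed fall is under about 8 points

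*Combined protocol and SAP*

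**What the plan says.** Under Statistical Analysis, Aim 4, the ratio is the "difference in per-capita cost of the intervention versus control group divided by the difference in their average effectiveness". The effect is the percentage of alters reporting any condomless intercourse, and the comparison is made "in the marginal cost of decreasing alters' condomless intercourse". As the terms are ordered, a fall in the intervention arm gives a positive denominator. The only statement on uncertainty is "We will estimate confidence intervals with bootstrap methods", with a literature citation.

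The section does not state the bootstrap variant, the unit to be resampled, or what happens to replicates whose denominator is zero or negative. It does not make the ratio conditional on a demonstrated effect. The documents mention no cost-effectiveness plane, net benefit or acceptability curve. The adjustment for correlation within index participants and session groups appears under the heading for Aims 1–3, not under Aim 4.

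The comparator is inconsistent. Aim 4 subtracts the cost of an attention control, and Recruitment and Statistical Power also refer to one. The Specific Aims, the trial Overview and the Protection of Human Subjects section describe a control arm that receives no intervention.

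**The concern.** A ratio is hard to order when its denominator may be zero. If the intervention costs more than control, a replicate with a small benefit gives a very large positive ratio, and one with a small harm gives a very large negative ratio. Every harmful replicate ranks below every beneficial one. A percentile interval taken directly on the ratio can therefore have a lower limit that looks like a saving but comes from replicates in which the intervention costs more and does worse.

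Aim 4 is meant to tell policymakers whether the programme is worth funding. If the effect on condomless sex is modest, the planned interval may not be readable as a range of cost per unit of benefit, and the plan does not say what would be reported in its place.

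**Working it through.** **Inputs.** From Statistical Power: "Based on the pilot, we assume 65% of control alters will report condomless sex at month 18"; effective sample 612 (ICC .01) or 568 (ICC .05); detectable differences 10.3 and 10.7 points. Allocation is 1:1 (Randomization). Assumed here, because the documents do not say: two-sided 5% level; the month-18 cross-sectional difference as the denominator; a positive cost difference, set at 100 arbitrary units with standard error 5.

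**The plan's own figures.** With 3.5 × 0.85 = 2.975 retained alters per index participant, 625/(1 + 1.975 × ICC) gives 613 and 569, matching the stated 612 and 568. The power claim is "we will have .80 power to detect a group difference of 10.3" points, to 54.7%. For 65% versus 54.7% with 306 per arm, the two-proportion formula gives .740, and .80 would need 710 alters in total. For 65% versus 75.3% it gives .797, so the stated figure reproduces only for an increase. The ICC .05 case behaves the same way (.740 for a 10.7-point fall, .799 for a rise). Both powers are carried forward.

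**Precision of the denominator.** With d the fall, n the effective total and p = .65 − d,

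SE = √[p(1 − p)/(n/2) + .65 × .35/(n/2)].

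At d = .103 this is 3.94 points (n = 612) or 4.09 points (n = 568).

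**Chance that the 95% interval for the effect includes zero:** Φ(1.96 − d/SE) − Φ(−1.96 − d/SE).

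| True fall | n = 612 | n = 568 |
|---|---|---|
| 10.3 points | 26% | 29% |
| 7 points (illustrative) | 57% | 60% |
| 5 points (illustrative) | 75% | 77% |

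At the 10.7 points that the plan pairs with n = 568, the figure is also 26%. If the stated .80 power is accepted, it is 1 − .80 = 20%.

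**When a percentile interval turns negative.** The share of harmful replicates is Φ(−d/SE), with d now the observed fall. It passes 2.5% when d < 1.96 × SE. Solving with SE at that d gives 1.96 × 3.93 = 7.7 points (n = 612) and 1.96 × 4.08 = 8.0 points (n = 568).

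**Two observed results,** in cost units per percentage point, from normal draws of cost and effect:

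| Observed fall | n | Harmful replicates | Percentile interval |
|---|---|---|---|
| 10.3 points | 612 | 0.4% | 5 to 35 |
| 10.3 points | 568 | 0.6% | 5 to 38 |
| 5 points | 612 | 10% | −162 to +197 |
| 5 points | 568 | 11% | −168 to +198 |

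In the third row the limits correspond to effects of 100/(−162) = −0.6 and 100/197 = +0.5 points. The interval therefore leaves out essentially only effects close to zero. It keeps clear harm: a 3-point worsening gives 100/(−3) = −33, well inside the limits.

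**Session groups.** The effective sample sizes allow only for clustering within index participants. With 7 intervention groups there are about 312.5/7 = 44.6 retained alters per group. Multiplying the intervention-arm variance by 1 + 43.6 × ICC, with assumed group ICCs of .01, .02 and .05, raises the 26% at 10.3 points (n = 612) to 34%, 42% and 57%.

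**The case against.** The strongest reply is that the plan does not commit to the method that fails. It says bootstrap and cites a source that cannot be consulted here, so that source counts neither for nor against it. The ranking problem belongs to percentile-type intervals computed on the ratio. A reader might infer that the plan will rank harmful replicates as cheapest; the text does not support that. What stands is that the variant and the handling of non-positive denominators are unspecified.

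A reader might also infer that the interval will be uninterpretable whatever the result. It will not: at an observed 10.3 points it is usable, and at a true 10.3 points 71–74% of trials would have an effect interval that excludes zero. The 7- and 5-point effects are illustrations, not plan values.

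The sign argument needs a positive cost difference. That is a reasonable expectation against a no-intervention arm, but the documents give no costs. Against a costed attention control the sign is unknown, and a negative ratio could mean cheaper and better. This objection stands; it makes the ratio harder to read, not easier.

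The standard error is a proxy, since Aim 4 states neither time point nor estimator. Baseline adjustment could reduce it and session-group correlation could increase it.

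Finally, condomless sex is an Aim 1 primary outcome with its own analysis, so policymakers would have other evidence of a null or harmful effect. That limits the damage but does not supply a valid interval for Aim 4.

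**Conclusion.** The concern holds in a conditional form. Aim 4 leaves open how its interval will be built and what happens when the effect difference is near or below zero. Under the month-18 power inputs, a two-sided 95% level and a positive cost difference, a percentile interval on the ratio takes in negative values that represent harm once the observed fall is below about 7.7–8.0 points. The effect interval includes zero in roughly one trial in four at the plan's own target effect, one in five on its stated power, and more than half if the true fall is 7 points. The trial's primary conclusions are not affected. The documents do not support saying that the planned interval is wrong in every case, or that the intervention certainly costs more than its comparator.

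**What to change.** Rewrite the Aim 4 inference before analysis:

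- Report incremental cost and incremental effect separately, each with its interval, and show the joint bootstrap scatter on the cost-effectiveness plane. State the time point and estimator of the effect.
- Base inference on incremental net benefit, λ × (effect difference) − (cost difference), and an acceptability curve over a pre-stated range of λ, the willingness to pay per alter without condomless sex. This involves no division, so it remains valid when the effect is near zero or negative.
- Resample whole index participants with their alters, within arm. Resample intact session groups as a sensitivity analysis only: 7 intervention groups are too few for a reliable bootstrap, although ignoring them may make the main interval too narrow.
- Give the ratio as a point estimate, with an interval only when the effect interval excludes zero, and name the bootstrap variant used.
- Reconcile the comparator across sections, because it determines the sign of the cost difference.

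No new data are needed. The cost is a little extra analysis and the need to name and defend a willingness-to-pay range, which the documents do not now give.
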